**10.4 Operative Data (If “Yes, performed at this institution” to ‘Was spinal surgery performed?’)**

Grade of most senior surgeon present in the operating theatre	
 
● Fully qualified spinal surgeon
 
● Other qualified surgeon
 
● Surgical trainee
 
● Medical doctor
 

Type of anaesthesia	
 
● General
 
● Local
 
● None
 

Grade of most senior anaesthesia provider present in the operating theatre	
 
● Fully qualified anaesthetist with medical qualification
 
● Anaesthetist in training with medical qualification
 
● Not medically qualified anaesthesia provider
 
● Anaesthetic administered by the surgeon
 

Date of Operation	dd/mm/yyyy
Duration of operation	
 
● Less than 1 hour
 
● 1-5 hours
 
● 5-10 hours
 
● Over 10 hours
 

Were pre-incision prophylactic antibiotics given?	
 
● Yes
 
● No
 

Class of surgical wound	
 
● I Clean
 
● II Clean-contaminated
 
● III Contaminated
 
● IV Dirty-infected
 

Location of surgery	
 
● Cranio-cervical
 
● Cervical
 
● Thoracic
 
● Lumbar
 
● Sacral
 

What was the main procedure undertaken?
 
*If >1 procedure undertaken, refer to the main one
 
** Flow-Chart on ORION Platform **
	
 
● Open 
 
a. Approach: Anterior/Posterior/360
 
b. Minimally invasive surgery? Yes/No
 
c. Open Reduction? Yes/No
 
d. Direct decompression? Yes/No
 
e. In situ fusion? Yes/no
 
f. Fusion? Yes/No 
 
▪ Type of instrumentation 
 
● None
 
● OC
 
● C1/2
 
● Lateral mass
 
● Pedicle
 
● Anterior plating
 
● Bone graft
 
● Intervertebral fusion
 
● Lateral plating
 
 
 
 
 
○ Fluoroscopy used: Yes/No
 
 
 
● Closed 
 
○ Gardener Wells vs Halo
 
○ Mechanism of Maintenance: Collar vs Halo vs Bedrest
 
 
 

Funding (Select all who contributed)	
 
● Patient
 
● Family
 
● Government
 
● Insurer
 
● Hospital
 
● NGO
 

	
 
• Other (specify _____)
 

Did the patient experience a hypotensive episode (systolic BP<90mmHg for >5 minutes) during the surgical procedure?	
 
• Yes
 
• No
 

Did the patient experience a hypoxic episode (SpO 2 < 90% for > 5 minutes) during the surgical procedure?	
 
• Yes
 
• No
 

Optional further comments regarding the procedure	Free text
Intraoperative complications (please select all that occurred)	
 
• None
 
• Incorrect level of surgery
 
• Misplacement of metalwork
 
• Incidental durotomy
 
• Death
 
• Other (specify _____)
 

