### **1.1 Primary Objective**

- Characterise case-mix, processes of care and variations in nonoperative and operative management strategies, including emergency, ward, surgical and ICU care, in patients presenting with traumatic spinal injury (TSI) between centres across low and high Human Development Index (HDI) countries

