### 4.2 Data Validation

A number of steps have been taken to ensure validation of all data entered.

- I. The dataset, web-based case report forms, and curation process has been designed according to DAQCOR principles.
- II. Web-based forms in the ORION platform contain fixed options at the point of data entry to maximise the likelihood of accurate and complete data capture at the point of collection.
- III. A local data validator independent to the local study team will be appointed at every participating institution. They will have access to a separate platform on Orion to ensure blinding to the rest of the data collected at their institution. They will be asked to complete a two-phase validation process, with a specific ORION validation user guide available to guide them through the process.
  - a. Prospective Case Acquisition: During the selected 4-week inclusion period, the local data validator will be asked to independently identify and collect all patient cases suitable for inclusion in the study. For validation, they will be required to prospectively collect these cases, recording the admission date, age at admission and AO injury type. This will subsequently be correlated with the data collected by their local team by the central study team.
  - b. Retrospective Operative Data: At 10 weeks from the start of the inclusion period (6-weeks following the end of the inclusion period), the local data validator will be asked to independently access operating theatre logs over the preceding 10 weeks. They will be required to document all the patients who have had an operation for TSI during this period and input the date and type of operation into the validation system where this corresponds to a patient admitted during the inclusion period. This will be used by the central study team to validate this specific cohort of their institution's cases.

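### As printed, the only structured implant field sits under the fusion item and mixes implants with graft, so fusion and instrumentation may not be separable in the operative data

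*Combined protocol and SAP*

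**What the plan says.** Section 10.4 of Appendix A asks for the main procedure. For open operations it lists approach, minimally invasive surgery, open reduction, direct decompression, then "e. In situ fusion? Yes/no" and "f. Fusion? Yes/No". Under the last of these, and nowhere else in the appendix, comes "Type of instrumentation". Its options include none, lateral mass, pedicle, plating, bone graft and "Intervertebral fusion". A fluoroscopy question follows at the outer level, directly under the open heading.

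The procedure question carries the note "Flow-Chart on ORION Platform", and that chart is not in the protocol. A later field, "Optional further comments regarding the procedure", is free text.

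Section 3.5 presents Appendix A as the complete data set. Section 4.2 says "Web-based forms in the ORION platform contain fixed options at the point of data entry". The primary objective in section 1.1 covers "variations in nonoperative and operative management strategies, including emergency, ward, surgical and ICU care", and section 5 plans a quantitative summary of operative management with variances compared within and between sites.

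**The concern.** Whether an implant was used and whether a fusion was done are two separate facts about an operation. The printed form makes the first a sub-question of the second. A patient stabilised with screws or a plate and no fusion has no obvious place on it. If the sub-list opens only after a yes to fusion, the site must either answer yes untruthfully to reach the implant list, or answer no truthfully and leave the implant out of the coded data.

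The option list has its own difficulty: it offers graft and intervertebral fusion as alternatives to implants, although they may be used together.

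At stake is the description of operative variation. If two sites with the same practice resolve the ambiguity differently, a coding habit appears as a difference in practice. There is also a denominator problem. Section 10.4 records misplaced metalwork and section 10.5 records metalwork removed for infection. The natural denominator for both is operations with an implant, which this layout may not supply reliably.

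**Working it through.** The plan states no figure on this point, so there is none to reproduce. The check is a reading of the form, followed by a bound.

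**1. Is there another place for an implant?** In sections 10.1 to 10.5, metalwork appears elsewhere only as a complication (misplacement, removal). No other structured field records an implant, and no item covers fixation or stabilisation without fusion. The in situ fusion item has no instrumentation list.

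**2. Is the list conditional on fusion?** The evidence points both ways.
- For: the same cell uses nesting alone as a condition. Items a to f apply only to open procedures, and the traction-device choice only to closed ones, with no printed condition. Fluoroscopy, meant for any open operation, sits at the outer level; instrumentation does not.
- Against: many sub-questions in sections 10.2, 10.3 and 10.5 are introduced by an explicit if-yes, and item f has none.
- Neutral: the none option fits either reading, as an uninstrumented fusion or as an operation without implants.

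Conditional is the more natural reading, but it is an inference.

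**3. Bound if the list is conditional.** Let f be the share of open operations that are fixation without fusion, and p the proportion of those that a site codes as fusion. Assume that a yes to fusion leads to the implant being entered, that free text is not coded, and that there is no other error.
- Observed fusion rate = true rate + p × f.
- Observed instrumentation rate = true rate − (1 − p) × f.
- The two errors sum to p × f + (1 − p) × f = f, so neither can exceed f.
- For two sites with the same practice, the spurious gap in either rate is |p₁ − p₂| × f. It equals f only when one site has p = 1 and the other p = 0.

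The documents give no value for f or p. Purely as an illustration, assume f between 0.10 and 0.30:

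| Coding pattern | f = 0.10 | f = 0.30 |
|---|---|---|
| p = 0.5: fusion rate too high by | 5 points | 15 points |
| p = 0.5: instrumentation rate too low by | 5 points | 15 points |
| Spurious gap, p₁ = 1 and p₂ = 0 (worst case) | 10 points | 30 points |
| Spurious gap, p₁ = p₂ | 0 | 0 |

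**4. What remains if the list is not conditional.** Fields meant to take several answers are marked as such for other injuries (10.1), imaged regions (10.2), funding and intraoperative complications (10.4) and adverse events (10.5). The instrumentation list is not marked. If it takes one answer:
- Screws plus graft: one of the two is lost. The fusion rate is unaffected. The instrumentation rate falls only where the site picks graft.
- Two implant types: the operation still counts as instrumented, but one type is lost.
- Graft without an implant: if any entry other than none is counted as instrumentation, the operation is wrongly counted as instrumented.

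**The case against.** The strongest reply is that the branching is defined by the platform flow-chart, which the protocol does not show. Indentation in a table is weak evidence of form logic, and nothing printed forbids a no to fusion together with a pedicle entry. This stands. A reader might infer that implants can be entered only after a yes to fusion, so that fixation must be miscoded. The documents do not support that certainty.

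Nor is the implant necessarily lost altogether, because the free-text comment could hold it. That also stands, but the comment is optional and uncoded, so it cannot support rates.

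A reader might also infer that both rates are wrong wherever these techniques are used. That does not follow. For each fixation-only operation, one rate or the other is affected, depending on the answer; with screws plus graft, the fusion rate stays correct.

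The absence of a multi-select mark is not proof of single choice. The inpatient therapy list in section 10.3 is also unmarked, although several therapies could be given. Hence the word appears.

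Finally, neither rate is a named outcome in section 3.5 or section 5, and section 6 says that the study is not designed to examine the efficacy of specific management. This limits the weight of the point. It does not remove it, because describing variation in operative management is part of the primary objective.

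**Conclusion.** The point holds in a limited form. As printed, the only structured implant field is nested under fusion, fixation without fusion has no item, and the list mixes implants with fusion elements in what appears to be a single choice. If the platform follows the page, some fixation-only operations will raise the fusion rate or lower the instrumentation rate, and sites may differ in which. If the platform does not gate the list, the loss from a mixed, apparently single-choice list remains.

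The size is unknown. The error from the nesting is bounded by the share of open operations that are fixation without fusion, which the documents do not give; the 10% to 30% range above is an assumption for illustration. A between-site gap equal to that share is a worst case that needs consistently opposite answers. The documents do not show that operative variation will in fact be misdescribed, only that the printed form permits it.

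**What to change.** Before launch, with the platform pilot in section 4.1 as the natural moment:

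1. Confirm how the platform branches from the fusion item and whether the instrumentation list takes more than one answer.
2. Take instrumentation out of item f and ask it for every open operation, marked as select all that apply, with the none option kept.
3. Move bone graft and intervertebral fusion to the fusion item, so that the instrumentation list holds implants only.
4. State in section 5 that fusion and instrumentation will be reported as two separate rates.

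The cost is a small edit to one part of the web form and one further question for open operations without fusion. It changes how operations are recorded, not how patients are treated. Timing matters: section 3.4 lets sites choose any 30-day window within six months, so an edit after the first sites have started would leave two form versions. In that case the version should be recorded with each case, and the affected fields summarised separately by version.

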## **5. Statistical Analysis**

Anonymised data will be analysed by the central study team. Fundamentally the main analysis will consist of a quantitative description of case-mix and the variations in processes of care. Identification and description of areas where known best practice is lacking or unavailable will be performed. This will enable identification of potential targets for future implementation studies.

In addition, early outcomes will be assessed to identify case-mix and process factors that may form a substrate for intervention. Participating centres will be stratified based on their country into groups based on their Human Development Index (HDI). The Human Development Index is calculated for each country based on its life expectancy at birth, years of schooling and gross national income (GNI) per capita.

Specifically, after data validation and curation, the primary analysis will comprise of (1) statistical descriptive analysis of patient-level registry variables, (2) characterisation of processes of care using statistical descriptions of both provider profiling data and patient-level process variables followed by a description of typical process groupings. This will follow and extend methodologies that have previously been applied successfully to traumatic brain injury. Case-mix and process analysis will be stratified in a nested way by site, country, and association with human development index (HDI).

Analysis for the secondary objectives will consist of a quantitative statistical summary of non-operative and operative management. Intra- and inter-site variances will be compared and associations with HDI and process of care factors sought.

Whilst only short-term outcomes can be obtained in this pragmatic point-study, outcomes analysis will be attempted for early mortality, functional status as assessed using the 5-point Frankel Grade, neurology, adverse events and trajectory from admission to 6 weeks post-injury (or discharge or death, whichever occurs first). These will be analysed by HDI group in an appropriate nested model accounting for random effects of site and country. Either ordinal models (for statistical power) or dichotomised models will be used depending on the statistical properties of the data and suitability of model assumptions. Mixed effects models will be used to assess the relationship between HDI and deterioration in functional status at 6 weeks while controlling for confounding variables.

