**10.2 Imaging Data**

Date/Time of first imaging	dd/mm/yyyy HH:MM
Most advanced type of imaging performed	
 
● Plain film radiograph
 
● Non-contrast CT Scan
 
● Contrast CT Scan
 
● MRI Scan
 

Anatomical area of spine included on imaging (Can select multiple)	
 
● Cervical
 
● Thoracic
 
● Lumbar
 
● Sacral
 

Level of fracture	
 
● Upper cervical
 
● Subaxial
 
● Thoracolumbar
 
● Sacral
 
● No injury
 

AO Classification of Injury	
Subluxation/Translation	
 
● Yes
 
● No
 

Traumatic herniated nucleus pulposis (not required if only plain radiograph available)	
 
● Yes
 
● No
 
 
If Yes:
 
 
● Please specify level:
 
● Cord compression: Yes/No
 

Haematoma (not required if only plain radiograph available)	
 
● Yes
 
● No
 

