### 10.5 Outcome Data

Death within the 6-week follow-up period?	
 
• Yes
 
• No
 
 
If Yes:
 
 
• Date of death: dd/mm/yyyy
 
• In ICU at time of death? Yes/No
 

Discharged within the 6-week follow-up period?	
 
• Yes
 
• No
 
 
If Yes:
 
 
• Date of discharge: dd/mm/yyyy
 
• Destination of discharge: 
 
○ Transfer to another hospital
 
○ Transfer to a rehabilitation unit
 
○ Usual place of residence/Home
 
○ Absconded
 
○ Other (specify _____)
 
 
 

Was the patient admitted to intensive care at any point during the 6-week follow up period?	
 
• Yes
 
• No
 
 
If Yes:
 
 
• Date of admission to ICU: dd/mm/yyyy
 
• Was the patient discharged from ICU during the 6-week follow up period? Yes/No
 
 
If Yes:
 
 
• Date of discharge from ICU: dd/mm/yyyy
 

Was the patient intubated during admission?	
 
• Yes
 
• No
 

Did the patient require a tracheostomy?	
 
• Yes
 
• No
 

Was the patient requiring ventilatory support at time of death/the end of the 6-week follow up period (whichever event occurs first)?	
 
• Yes
 
• No
 

Did any adverse events of special interest occur in the 6-week follow-up period? (Select all that apply)	
 
• None
 
• Pressure Ulcer
 
• Pneumonia
 
• Pulmonary embolism
 
• Deep venous thrombosis
 
• Decubitus Ulcer
 

	
 
• Urinary tract infection
 
• Symptomatic haematoma
 
			
Did any surgical site infections occur in the 6-week follow-up period?	
 
• Yes
 
• No
 
 
If Yes:
 
 
• Required antibiotics only
 
• Required debridement
 
• Required removal of metalwork
 
			

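### Intra-operative hypoxia and hypotension can be answered only Yes or No, so an unmonitored operation would probably be recorded as 'No' or left blank

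*Combined protocol and SAP*

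**What the plan says.** Section 10.4 of Appendix A contains two intra-operative safety items. One begins "Did the patient experience a hypoxic episode" and sets the criterion at SpO2 below 90% for more than 5 minutes. The other reads "Did the patient experience a hypotensive episode (systolic BP<90mmHg for >5 minutes) during the surgical procedure". The printed answers to each are Yes and No. No other field in section 10.4 records whether oxygen saturation or blood pressure was monitored or charted during the operation.

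Four other parts of the plan bear on this:

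- **Data entry.** Section 4.2 says the ORION web forms "contain fixed options at the point of data entry to maximise the likelihood of accurate and complete data capture". In section 10.4 the only field labelled optional is the free-text one, "Optional further comments regarding the procedure".
- **Items that cannot be assessed.** The form allows for these elsewhere. In section 10.2 the herniated disc and haematoma items are "not required if only plain radiograph available". In section 10.1 the injury-level items accept an 'Unknown' answer.
- **Validation.** The operative check in section 4.2 collects only the date and type of operation.
- **Analysis.** Section 3.5 lists intra-operative course and complications among the operative measures. Section 5 describes registry variables and stratifies case-mix and process results by site, country and HDI. It gives no rule for missing answers.

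**The concern.** Each item can be answered properly only if repeated readings were taken, because the criterion combines a threshold with a duration. Where there was no oximeter, no cuff or no chart, the true answer is that nobody knows, and the form has no structured place for that. 'No' is the most natural choice; leaving the item blank is the other.

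Such operations are foreseeable. Section 3.1.1 opens the study to institutions at every level, including those where non-physicians manage the injury. Section 10.4 lists operations done without anaesthesia, with the surgeon giving the anaesthetic, or with a "Not medically qualified anaesthesia provider". These options do not show that monitoring was absent. They do show that it cannot be taken for granted.

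What is at stake is the comparison between well and poorly equipped sites. If 'not measured' is stored as 'did not happen', the least equipped sites look safer than they are. If it is stored as a blank, the missing answers cluster at those sites and the plan does not say how to treat them. In both cases the absence of monitoring, itself a gap in care of the kind the study sets out to find, goes unrecorded for the individual operation.

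**Working it through.** The plan gives no hypoxia or hypotension rate, no monitored share and no sample size, so there is no figure of its own to reproduce. The following is an illustration.

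**Inputs from the documents.** Two items, two answers each, and no per-operation record of monitoring (section 10.4).

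**Assumed inputs.** True event rate p = 10% at every site. Share of operations monitored m = 95% at high-HDI sites and 70% at low-HDI sites, with 50% to 90% as the range for the latter. There are no false positives, and risk is the same with and without monitoring.

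**Case 1: every unmonitored operation is entered as 'No'.** Recorded rate = p × m.

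- High-HDI: 10% × 0.95 = 9.5%.
- Low-HDI: 10% × 0.70 = 7.0%.
- Ratio: 7.0 / 9.5 = 0.74, with no true difference.

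| Monitored at low-HDI sites | Recorded rate | Ratio to 9.5% |
|---|---|---|
| 50% | 5.0% | 0.53 |
| 70% | 7.0% | 0.74 |
| 90% | 9.0% | 0.95 |

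When true rates are equal, p cancels and the ratio is 0.70 / 0.95 whatever its value. With p = 20% the recorded rates are 19% and 14%, and the ratio is again 0.74.

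**Case 2: every unmonitored operation is left blank.** The rate among completed answers is p × m / m = p, so 10% in both groups. The missing share is 1 − 0.95 = 5% against 1 − 0.70 = 30%. The rate is unbiased only if risk does not depend on monitoring. The cause of the blanks is not recorded.

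**Mixed practice.** If sites do some of each, the ratio lies between 0.74 and 1.00, and the stored data cannot show where.

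**With a third option.** The rate among monitored operations returns to p (10% and 10%), and the unmonitored shares of 5% and 30% become visible results.

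**The case against.** The strongest reply is that the documents do not say what a site does when there was no monitoring. The items are not stated to be mandatory, the free-text field could carry an explanation, and Appendix A lists data fields rather than showing the live form. This stands. It is why the point says 'probably' and allows for blanks. It does not remove the problem, since blanks would be concentrated at poorly equipped sites without a handling rule.

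Provider profiling (section 3.2) asks about surgical-phase resources, a pilot is planned (section 4.1), and clinicians from low-HDI countries helped to develop the dataset (section 3.3). These are partial safeguards. Profiling is at site level and is not shown to cover monitoring, so it cannot tell which operations were monitored.

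A reader might also infer three stronger points that the documents do not support:

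- **That the HDI outcome model is biased.** The sentence "These will be analysed by HDI group in an appropriate nested model accounting for random effects of site and country" refers to mortality, function, neurology, adverse events and trajectory. Intra-operative hypoxia and hypotension are not among the outcomes listed in section 3.5, nor among the adverse events of special interest in section 10.5.
- **That the HDI association is reversed.** With equal true rates the error can create a difference but has none to reverse. Reversal needs a higher true rate at low-HDI sites as well. With 15% against 10% and 95% monitored at high-HDI sites, for example, it needs fewer than 0.095 / 0.15 = 63% monitored at low-HDI sites. None of these figures is in the documents.
- **That a tick for how the diagnosis was made would cure the same ambiguity for deep venous thrombosis and "Pulmonary embolism".** Such a tick applies only to events already selected. It cannot separate 'absent' from 'could not be looked for', so it is not proposed.

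**Conclusion.** The point holds as a defect of the data form. Two measurement-based items have no answer for an operation in which the measurement was not made, and no part of the validation or analysis plan recovers that information. The likely effect is a recorded rate that is too low, or answers that are selectively missing, at the least equipped sites. It is confined to the descriptive intra-operative results by site, country and HDI.

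The size cannot be found from the documents. The ratio of 0.74 (0.53 to 0.95) rests on assumed monitored shares, on every unmonitored operation being entered as 'No', and on risk being unrelated to monitoring. If some of those operations are left blank, the distortion in the rate is smaller and the missing-data problem larger. The change is worth making because it is cheap, follows the form's own practice for imaging items, and cannot be made up for once answers have been stored as Yes or No.

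**What to change.** Add 'Not monitored / no record' as a third answer to both items in section 10.4. In section 5, state that event rates for these items are calculated among monitored operations, and that the unmonitored share is reported by site and HDI group as a process-of-care result.

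The cost is one more option on two items, a denominator rule and one extra line in the tables. The pilot in section 4.1 is a natural point to make the change.

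There are two downsides. Denominators become smaller. The rate among monitored operations may also be selective if monitoring depends on the type of case, for example if it is used more often under general anaesthesia than under local or none. Reporting the rates by type of anaesthesia, which section 10.4 already collects, would show part of this selection without any new data.
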